8.7 Examination of Subgroups

Subjects will be categorized into subgroups based on whether they had previously been treated with talimogene or another oncolytic viral vector prior to enrollment in this study (yes or no). Another subgroup of interest is subjects with prior anti-PD-(L)1 as monotherapy or in combination therapy (e.g., prior treatment with nivolumab + ipilimumab) or subjects with prior CTLA-4; subjects will be categorized into subgroups based on such prior combination therapy (yes or no). ORR and DRR using RECIST v1.1 and irRECIST will be analyzed by these subgroups if the data support such analyses.

Subjects will be categorized into subgroups based on whether or not they received CYP substrate concomitant medications.

Subjects will be categorized into subgroups based on whether they had previously been treated with Oncolytic Virus, CTLA-4 Inhibitor monotherapy in metastatic setting, CTLA-4 Inhibitor monotherapy, PD-(L)1 Inhibitor monotherapy, CTLA-4 + PD-(L)1 Inhibitor combination or, Other PD-(L)1 combination in the Previous Melanoma Treatment eCRF page; subjects can be in more than one subgroup. ORR, DRR, DCR, and BOR using RECIST and irRECIST will be analyzed by these subgroups if the data support such analyses.

Other subgroups of interest are baseline LDH (elevated or not); disease stage (IV or earlier stage, Stage M1c); BRAF mutation positive with prior targeted therapy, BRAF mutation positive with no prior targeted therapy, BRAF wild type; 8 mg IMO-2125 and ipilimumab combination dose group; subjects without any major protocol deviations; subjects who received at least 1 dose of IMO-2125 and 2 doses of ipilimumab in combination in any phase; and duration of prior anti-PD-1 therapy (≥ 12 weeks and < 12 weeks). Subjects with unknown baseline LDH status will not be included in the subgroup analysis. Targeted therapy is either a BRAF or MEK inhibitor,

or both. Prior anti-PD-1 therapy is PD(L)-1 Inhibitor. ORR, DRR, DCR, and BOR using RECIST and irRECIST will be analyzed by these subgroups if the data support such analyses.

8.8 Multiple Comparison/Multiplicity

The study Type I error rate is split between the phase 2 hypothesis tests for each treatment arm, so that the ORR is tested at the 0.025 significance level for each.

9 METHODS OF EFFICACY ANALYSIS

9.1 Phase 1

Efficacy reporting will consist of listings of the best overall response by irRC and RECIST v1.1 and change in tumor burden (sum of the longest diameters).

9.2 Primary Efficacy Analyses

The primary efficacy endpoint, investigator-assessed ORR using RECIST v1.1, will be analyzed for all subjects in the PPIEE population and the first 21 patients in the PIIEE, as well as the PIIEE population and SIIIEE population combined using a one-sided, one sample exact binomial test with $\alpha = 0.025$ in each test. The proportion of subjects achieving a best confirmed response of CR or PR will be tested against the null rates of 0.11 and 0.05 for ipilimumab and pembrolizumab, respectively (Hodi et al, 2010).

The primary efficacy analyses will test the following hypotheses:

H_0 : The ORR assessed using the RECIST v1.1, for subjects in the IMO 2125 + ipilimumab treatment arm, is no larger than 0.11;

H_1 : The ORR assessed using the RECIST v1.1, for subjects in the IMO 2125 +ipilimumab treatment arm, is at least 0.35.

H_0 : The ORR assessed using the RECIST v1.1, for subjects in the IMO 2125 +pembrolizumab treatment arm, is no larger than 0.05;

H_1 : The ORR assessed using the RECIST v1.1, for subjects in the IMO 2125 +pembrolizumab treatment arm, is at least 0.35.

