Each cohort will be monitored for the occurrence of DLTs. The DLT evaluation period will be Cycle 1 (Weeks 1 through 4). If a subject discontinues study participation before the DLT evaluation period is finished due to reasons other than experiencing a DLT, that subject must be replaced so that the cohort may be properly evaluated. More information about the review of DLTs and the escalation of dose levels between cohorts is provided in Section 3.1.3, Section 3.1.4, and Section 3.1.5.

There are 3 subjects planned per cohort. During Phase 1, the sponsor will assign subjects to a treatment arm (IMO-2125 + ipilimumab or IMO-2125 + pembrolizumab) by cohort.

After completing the DLT evaluations for all planned IMO-2125 doses in either combination, supplemental cohorts of up to 5 subjects each may be enrolled with either combination at doses up to and including the MTD. After completion of either Phase 1 treatment arm and determination of the RP2D for that arm, the Phase 2 portion for the

completed treatment arm may be initiated. It is not necessary for Phase 1 to be completed in both treatment arms before Phase 2 is started.

3.1.2 Phase 2

The Phase 2 portion of the study will assess preliminary efficacy, using investigator-assessed RECIST v1.1, of IMO-2125 + ipilimumab, IMO-2125 + pembrolizumab, and any additional combinations that are studied in Phase 1. The dose level of IMO-2125 to be administered for each treatment arm will be the RP2D for the combination, as determined in Phase 1. Phase 2 will enroll up to 60 subjects treated at the IMO-2125 + ipilimumab RP2D. This will include at least 21 subjects in the primary IMO-2125 + ipilimumab efficacy-evaluable population and up to 20 subjects in the secondary IMO-2125 + ipilimumab efficacy-evaluable population. In the IMO-2125 + pembrolizumab Phase 2 cohort, enrollment will continue until 21 subjects in the IMO-2125 + pembrolizumab efficacy-evaluable population have been treated at the IMO-2125 + pembrolizumab RP2D. Phase 1 subjects treated at the RP2D for either combination may contribute to these totals. A two-stage design will be used to test for clinically and statistically relevant clinical activity. A treatment arm will stop if an interim futility analysis shows there is insufficient evidence of a clinically relevant response rate after 10 subjects (Stage 1).

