If a subject discontinues treatment before completing at least one efficacy evaluation for reasons other than toxicity, then that subject will be replaced with the replacement assigned to the same treatment arm and dose level as the subject who dropped out early.

Combination therapy in Phase 2 will continue using the same schedule as Phase 1 (see **Table 1**).

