The IMO-2125 + pembrolizumab treatment arm will use a two-stage design with a targeted Type I error rate of 0.025 to test the null response rate against the alternative of at least 35%. If at least 1 subject has an RECIST v1.1 response in Stage 1, then the treatment arm will continue to Stage 2 and treat 11 additional subjects. If at least 4 of the 21 total subjects have an RECIST v1.1 response, then the null hypothesis H_0 will be rejected in favor of the alternative H_a . In this treatment arm, this design has statistical power of 96%, an expected sample size of 14.41, and a probability of stopping at the end of the first stage of 60% if the response proportion is ≤ 0.05 .

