5. GENERAL ANALYSIS CONSIDERATIONS

The statistical analyses will be reported using summary tables, listings, and figures (TLFs). The International Conference on Harmonisation (ICH) numbering convention will be used for all TLFs. Unless otherwise noted, all statistical testing will be one-sided and will be performed at the 0.025 significance level. Tests will be declared statistically significant if the calculated p-value is less than or equal to the significance level of the test, usually 0.025. Continuous variables will be summarized with means, standard deviations, medians, minimums, and maximums. For continuous variables, descriptive statistics will include the number of non-missing values, mean, standard deviation, median, 25th and 75th percentile, minimum, maximum, and 95% confidence intervals (CIs) as appropriate. All durations will be reported in months.

For categorical variables, descriptive statistics will include counts and percentages per category. Statistics describing time-to-event variables will use the Kaplan-Meier method. Individual subject data obtained will be presented by subject in data listings. Dose group will be used to identify the dose and study treatment cohort in the Phase 1 portion of the trial; treatment arm will identify the treatment arm in the Phase 2 portion of the study. All analysis will be done using these descriptors.

The analyses described in this plan are considered *a priori*, in that they have been defined prior to database lock. All analyses and tabulations will be performed using SAS® Version 9.2 or higher. Tables and listings will be presented in RTF format. All SAS® programs will be validated by an independent programmer. In addition, all program output will undergo a senior level statistical review. The validation process will be used to confirm that statistically valid methods have been implemented and that all data manipulations and calculations are accurate. Checks will be made to ensure accuracy, consistency with this plan, consistency within tables, and consistency between tables and corresponding data listings. Upon completion of validation and quality review procedures, all documentation will be collected and filed by the project statistician or designee.

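### For pembrolizumab, the 4-of-21 rule and the exact test on an uncapped PPIEE population can disagree at boundary response counts if the population exceeds 21

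*SAP*

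**What the plan says.** SAP Section 4 gives the pembrolizumab arm a two-stage design: 10 subjects, continuation if at least one responds, then 11 more. The final rule is "If at least 4 of the 21 total subjects have an RECIST v1.1 response", in which case the null hypothesis is rejected.

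Section 9.2 defines the primary test differently. ORR by RECIST v1.1 "will be analyzed for all subjects in the PPIEE population and the first 21 patients in the PIIEE", "using a one-sided, one sample exact binomial test with $\alpha = 0.025$ in each test", against "null rates of 0.11 and 0.05 for ipilimumab and pembrolizumab, respectively". Section 5 adds the criterion: "Tests will be declared statistically significant if the calculated p-value is less than or equal to the significance level of the test". Section 8 repeats the asymmetry, with the ipilimumab test limited to the first 21 and the pembrolizumab test run on the whole population.

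Three other sections bear on the size of that population:

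- **Section 6** defines PPIEE as everyone treated at the RP2D of the combination, in either phase, with at least one dose of each drug. It sets no upper limit and requires no post-baseline scan.
- **Section 3.1.2** plans to enroll this arm until 21 efficacy-evaluable subjects have been treated. It also provides that, when a subject stops before one efficacy evaluation for reasons other than toxicity, "that subject will be replaced with the replacement assigned to the same treatment arm and dose level".
- **Section 8.4** counts subjects who leave the study without an on-study tumor evaluation as non-responders.

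**The concern.** The arm has two stated decision rules for one primary hypothesis. One is a fixed count out of 21. The other is a p-value computed on however many subjects PPIEE holds. The SAP does not say which governs if the two part.

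The plan's own rules allow more than 21. Pembrolizumab starts in Week 2 and the first response assessment is at Week 8 (Tables 1 and 5). A subject who leaves between those points for a reason other than toxicity has met the PPIEE definition, so stays in the population, and is also replaced. Over-enrollment has the same effect.

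At stake is the arm's primary conclusion. In an open-label trial with investigator-assessed response, the choice between two rules should not be left until the response counts are known.

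**Working it through.** **Inputs.** Null rate 0.05 and one-sided level 0.025 (Section 9.2); alternative 0.35, Stage 2 size 11, continuation at 1 or more responders and rejection at 4 or more of 21 (Section 4); Stage 1 size 10 (Section 3.1.2).

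**1. The plan's own figures.** Let X1 be the responders among the first 10 and X2 those among the next 11.

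- Early stop at 0.05: 0.95^10 = 0.599 (SAP: 60%).
- Expected size: 10 + 11 × (1 − 0.5987) = 14.41 (SAP: 14.41).
- Type I error: the sum over x ≥ 1 of P(X1 = x) × P(X2 ≥ 4 − x) = 0.3151 × 0.0152 + 0.0746 × 0.1019 + 0.0105 × 0.4312 + 0.0010 = 0.0180.
- Power at 0.35, by the same sum: 0.959 (SAP: 96%).

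The Section 4 design is reproduced.

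**2. The Section 9.2 test by population size.** The p-value for r responders among N is P(X ≥ r | N, 0.05).

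| N | r = 3 | r = 4 | r = 5 | Responders needed |
|---|---|---|---|---|
| 21 | 0.0849 | 0.0189 | 0.0032 | 4 |
| 22 | 0.0948 | 0.0222 | 0.0040 | 4 |
| 23 | 0.1052 | 0.0258 | 0.0049 | 5 |

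The requirement stays at 5 for N from 23 to 33. At N = 21 the two rules coincide for every count.

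**3. Where they part.**

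- N = 22: 3 of the first 21 plus a response in the 22nd subject gives 4/22, p = 0.0222. Section 9.2 rejects; Section 4 does not.
- N = 23: 4 of the first 21 and none in the other two gives 4/23, p = 0.0258. Section 4 rejects; Section 9.2 does not.
- N = 23: 3 of the first 21 plus both others gives 5/23, p = 0.0049. Section 9.2 rejects; Section 4 does not.

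**4. How often.** Let S be the responders among the first 21 in trials that pass Stage 1, so that P(S = s) = C(21,s) p^s (1−p)^(21−s) − (1−p)^10 × C(11,s) p^s (1−p)^(11−s). With two extra subjects who respond at the same rate p, the chance of disagreement is P(S = 4)(1−p)² + P(S = 3)p².

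| True ORR | P(S = 4)(1−p)² | P(S = 3)p² | Total |
|---|---|---|---|
| 5% | 0.01478 × 0.9025 = 0.0133 | 0.05784 × 0.0025 = 0.0001 | 1.3% |
| 15% | 0.18068 × 0.7225 = 0.1305 | 0.21093 × 0.0225 = 0.0047 | 13.5% |
| 20% | 0.20374 × 0.64 = 0.1304 | 0.16789 × 0.04 = 0.0067 | 13.7% |
| 35% | 0.05601 × 0.4225 = 0.0237 | 0.02143 × 0.1225 = 0.0026 | 2.6% |

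At N = 22 the chance is P(S = 3) × p: 0.05784 × 0.05 = 0.3% at 5%, 0.16789 × 0.20 = 3.4% at 20%, and 0.02143 × 0.35 = 0.8% at 35%.

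**5. Sensitivity.** If both extra subjects are replaced dropouts counted as non-responders, and Section 4 is applied to the other 21, only the first term remains, without its (1−p)² factor: 1.5% at 5%, 18–20% at 15–20%, and 5.6% at 35%.

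**The case against.** The best defense is that the plan intends the two sets to be the same. Section 3.1.2 stops pembrolizumab enrollment at 21 efficacy-evaluable subjects, and Section 8.6 ties the analysis of each Phase 2 arm to the 21 used in the two-stage design. The ipilimumab arm needs a cap because it plans at least 21 primary-evaluable subjects; the pembrolizumab arm does not plan to go further. This explains the asymmetry, and it stands: the conflict needs an unplanned overrun, whose size the SAP does not give.

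The replacement route is also narrow. A subject who leaves before the first pembrolizumab dose was never in PPIEE, so the replacement only restores the count. Only subjects who had both drugs and left before an efficacy evaluation add to it.

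Three stronger readings are tempting, and the documents do not support them:

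- **That the rules give opposite verdicts whenever 23 or more subjects are in the population.** They differ only at the boundary counts above, and 23 is not the first size at which they can differ.
- **That Phase 1 subjects push the count past 21.** Section 3.1.2 lets those treated at the RP2D count towards the totals.
- **That error control or power suffers materially.** The Section 9.2 test stays below 0.025 at every size. Rejecting whenever either rule rejects would give 0.0180 + 0.0029 = 0.0208 at N = 22 and 0.0180 + 0.0001 = 0.0181 at N = 23. Single-stage power at 35% falls from 96.7% at N = 21 to 94.5% at N = 23, but is 97.6% at 22 and 96.8% at 25.

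What the defense does not answer is that PPIEE has no cap, the replacement rule can take it past 21, and no text says which rule then decides.

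**Conclusion.** The point holds as a conflict between two stated decision rules for a primary hypothesis, conditional on PPIEE exceeding 21. At the planned size there is no conflict. With one extra subject, Section 9.2 can reject where Section 4 does not; with two, disagreement can run either way. At 23 subjects the chance of disagreement is about 1.3% at the null rate, 13–14% at a true rate of 15–20%, and 2.6% at the target rate.

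These chances assume independent responses at one common rate, the Stage 1 stop applied as written, and extra subjects who respond like the rest. The threshold of 23 rests on the ordinary exact binomial test that Section 9.2 names. A p-value allowing for the Stage 1 stop would be 0.0240 for 4 responders at N = 23 and 0.0273 at N = 24, which moves the threshold to 24. The chance of an overrun cannot be derived from the SAP.

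The matter is one of ambiguity in the primary decision, not of inflated error. It is worth settling in advance because the remedy is small.

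**What to change.** In Sections 8 and 9.2, limit the confirmatory pembrolizumab test to the first 21 subjects in PPIEE, as is already done for the primary ipilimumab population. State how the order is set, for example by date of first dose. Report the ORR in all PPIEE subjects with an exact confidence interval, descriptively.

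With the cap, the exact test needs 4 of 21 (p = 0.0189, against 0.0849 for 3 of 21), so the final thresholds in Sections 4 and 9.2 coincide.

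The cost is a few words in the SAP. Subjects beyond the 21st do not enter the hypothesis test. A replaced subject who falls within the first 21 counts as a non-responder in it, and a replacement ranked after the 21st does not count.

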4. DETERMINATION OF SAMPLE SIZE

The primary objective of Phase 2 is to assess the preliminary clinical activity, defined as the investigator assessed RECIST v1.1 ORR, of IMO-2125 in combination with ipilimumab or of IMO-2125 in combination with pembrolizumab in subjects with progression on or following PD-(L)1 therapy for metastatic melanoma. Given that two primary hypotheses are being tested (regarding the ORR of IMO-2125 and ipilimumab and the ORR of IMO-2125 and

pembrolizumab), a Bonferroni correction has been applied to the alpha to control for Type I error for the trial.

Assuming the immune-related ORR for subjects who receive ipilimumab alone is at most 11% (the historical response rate in subjects who are PD-1 inhibitor naïve), and a target immune-related ORR of 35% for subjects who receive the IMO-2125 ipilimumab combination treatment, a sample size of 21 subjects would achieve 77% power to detect a 24% difference in response rates using a one-sided significance level of 2.5%.

The IMO-2125 + ipilimumab treatment arm will use a two-stage design with a targeted Type I error rate of 0.025 to test the null response rate of 0.11 against the alternative of at least 35%. With this method, 10 subjects will be treated and monitored for an RECIST v1.1 response in the first stage. For this arm, if 2 or more subjects have an RECIST v1.1 response in Stage 1, then the treatment arm will continue to Stage 2, in which 11 more subjects will be treated. If at least 6 of the 21 total subjects have an RECIST v1.1 response, then the null hypothesis H_0 will be rejected in favor of the alternative H_a . In this treatment arm, this design has statistical power of 77%, an expected sample size of 13.33, and a probability of stopping at the end of the first stage of 69.7% if the response proportion is ≤ 0.11 .

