6. ANALYSIS POPULATIONS

The following analysis population will be used for safety analyses:

- Safety Population: all patients who received at least one dose of IMO-2125.

The following analysis population will be used only for Cohort Review Committee meetings to determine if the dose may be escalated.

- DLT Evaluable Population: all patients in the Safety Population who continue participation in the study for the entire DLT evaluation period, or who discontinue prematurely due to a DLT.

The following analysis populations will be used for efficacy analyses:

- Primary Ipilimumab + IMO-2125 Efficacy Evaluable (PIIEE) Population: all patients who are ipilimumab-naïve on study entry (including those who received ipilimumab only in the adjuvant setting) and who are treated at the RP2D for the IMO-2125 + ipilimumab combination, regardless of which phase of the study they receive it; and who received at least one dose of each study drug.
- Secondary Ipilimumab + IMO-2125 Efficacy Evaluable (SIIIE) Population: all patients who are not ipilimumab-naïve on study entry and who are treated at the RP2D for the IMO-2125 + ipilimumab combination, regardless of which phase of the study they receive it; and who received at least one dose of each study drug.
- Primary Pembrolizumab + IMO-2125 Efficacy Evaluable (PPIEE) Population: all patients who are treated at the RP2D for the IMO-2125 + pembrolizumab combination, regardless of which phase of the study they receive it; and who received at least one dose of each study drug.

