8. EFFICACY ANALYSES

The primary analysis of efficacy in the Phase 2 IMO-2125 + ipilimumab arm, including the hypothesis test of the ORR, will be performed on the first 21 patients in the PIIIE Population as defined in Section 6. An analysis of those in the SIIIE Population will also be performed; efficacy analysis in the combined PIIIE and SIIIE Population may also be summarized. The primary analysis of efficacy in the Phase 2 IMO-2125 + pembrolizumab arm will be performed on the PPIIE Population as defined in Section 6.

Patients will be categorized into subgroups based on whether they had previously been treated with talimogene or another oncolytic viral vector prior to enrollment in this study for some analyses.

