12 CHANGES TO PROTOCOL-SPECIFIED ANALYSES

The efficacy analysis in the combined PIIIE and SIIIE Population are added.

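### SAP Section 9.2 tests the combined ipilimumab populations as a third primary test at one-sided 0.025, so the 0.025 promised to that arm is not guaranteed

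*SAP*

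**What the plan says.** **Section 4** counts the primary hypotheses ("Given that two primary hypotheses are being tested"), one per combination, and applies a Bonferroni correction. For the ipilimumab arm it gives a two-stage rule: continue if at least 2 of 10 respond, then reject the 0.11 null if at least 6 of 21 respond. The null is justified this way: "Assuming the immune-related ORR for subjects who receive ipilimumab alone is at most 11" per cent.

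**Section 8.8** splits the study error between the arms, "so that the ORR is tested at the 0.025 significance level for each".

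**Section 8** places the ipilimumab hypothesis test on the first 21 subjects of the primary (ipilimumab-naive) population. Of the combined primary and secondary set it says only: "efficacy analysis in the combined PIIIE and SIIIE Population may also be summarized".

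**Section 9.2**, headed as the primary efficacy analyses, names three sets to be tested: the pembrolizumab population, the first 21 primary ipilimumab subjects, "as well as the PIIEE population and SIIIEE population combined using a one-sided, one sample exact binomial test". Alpha is 0.025 in each test, and the only ipilimumab null is 0.11. Two hypothesis pairs follow, one per arm.

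**Section 12** notes: "The efficacy analysis in the combined PIIIE and SIIIE Population are added". It gives that analysis no status and no share of alpha.

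The SAP spells the population labels in more than one way; PIIEE and SIIIE are used below.

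**The concern.** The alpha allocation covers two tests, but Section 9.2 runs three. Two of the three address the same arm against the same null, each at the full 0.025. If a rejection on either counts as a primary success, the arm's false-positive rate is that of the union of the two tests, which nothing in the plan holds to 0.025.

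Two further problems follow.

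- **Conflicting answers.** Section 9.2 gives both ipilimumab tests the same heading and level, with no rule for a case where one rejects and the other does not.
- **Unsupported null.** Section 4 supports 0.11 as a rate for ipilimumab alone. The "Secondary Ipilimumab + IMO-2125 Efficacy Evaluable (SIIIE) Population" consists of subjects who are not ipilimumab-naive at entry. The SAP gives no reason why 0.11 is the right reference for them, or for a mixture that includes them.

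A smaller, separate mismatch: Section 9.2 tests all pembrolizumab efficacy-evaluable subjects, whereas Section 4 states that arm's rule as at least 4 of exactly 21.

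**Working it through.** **Inputs from the SAP.** Ipilimumab arm: n1 = 10, continue if x1 ≥ 2; n = 21, reject if x1 + x2 ≥ 6; null 0.11, alternative 0.35 (Section 4). Up to 60 subjects at the ipilimumab RP2D, at least 21 of them primary and up to 20 secondary (Section 3.1.2). The Stage 1 stop is binding: "A treatment arm will stop if an interim futility analysis shows there is insufficient evidence" (Section 3.1.2). Pembrolizumab arm: at least 1 of 10, then at least 4 of 21; null 0.05.

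**Assumptions.** The final combined size N is not fixed, so every N from 22 to 60 is examined. The true ORR in ipilimumab-experienced subjects is not given; it is set first to 0.11, then varied.

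**Step 1: reproduce the stated design.** With x1 ~ Bin(10, p) and x2 ~ Bin(11, p):

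- P(stop at Stage 1 | 0.11) = P(x1 ≤ 1) = 0.697; the SAP says 69.7%.
- Expected N = 10 + 11 × (1 − 0.6972) = 13.33; the SAP says 13.33.
- Power at 0.35 = P(x1 ≥ 2 and x1 + x2 ≥ 6) = 0.773; the SAP says 77%.
- Exact Type I error at 0.11 = 0.0206, within 0.025.

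The pembrolizumab design also reproduces (power 0.959, expected N 14.41, stopping probability 0.599), with exact Type I error 0.0180.

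**Step 2: add the combined test.** It rejects at the smallest c with P(Bin(N, 0.11) ≥ c) ≤ 0.025. This gives c = 10 at N = 41, 11 at N = 52 and 13 at N = 60. With the stop binding, it is run only if x1 ≥ 2.

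**Step 3: chance of at least one false ipilimumab rejection**, ORR 0.11 in all subjects:

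| Combined N | Either test rejects |
|---|---|
| 22 | 0.0206 |
| 28 | 0.0223 |
| 41 (21 + 20) | 0.02496 |
| 52 (maximum) | 0.0313 |
| 60 | 0.0258 |

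The value exceeds 0.025 at 27 of the 39 sizes (69%). It moves up and down with N because c is an integer.

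**Step 4: lower ORR in ipilimumab-experienced subjects** (up to 20 of them; 0.11 in the rest):

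| ORR in experienced subjects | Peak over N | Sizes above 0.025 (of 39) |
|---|---|---|
| 0.10 | 0.0288 | 17 |
| 0.09 | 0.0267 | 8 |
| 0.08 | 0.0250 (marginally above) | 2 |
| 0.05 | 0.0221 | 0 |

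**Step 5: study-wide error.** With independent arms, error = 1 − (1 − union)(1 − 0.0180). For the two designed tests: 1 − (1 − 0.0206)(1 − 0.0180) = 0.038. At the N = 52 peak: 1 − (1 − 0.0313)(1 − 0.0180) = 0.0487. Both are below 0.05.

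**Step 6: disagreement at N = 41**, stop binding. P(only the first-21 test rejects) = P(either) − P(combined). P(only the combined test rejects) = P(either) − P(first-21).

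- ORR 0.35 primary, 0.05 secondary: 0.7733 − 0.3057 = 0.47, only the first-21 test rejects.
- ORR 0.35 primary, 0.11 secondary: 0.7792 − 0.4865 = 0.29, only the first-21 test rejects.
- ORR 0.25 in all subjects: 0.5628 − 0.4100 = 0.15, only the combined test rejects.

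**Step 7: pembrolizumab (minor).** P(X ≥ 4 | 0.05) is 0.0189 at n = 21, 0.0222 at n = 22 and 0.0258 at n = 23. The exact test and the 4-responder rule part company only from n = 23.

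**The case against.** The best defence is that the plan as a whole already shows which test decides. Section 8 puts the hypothesis test on the first 21 subjects, Section 4 gives the rule for 21, Section 9.2 lists only two hypothesis pairs, and the added subjects are labelled secondary. On that reading the combined test is supportive and Section 9.2 has one loose sentence. This may well be the intent. But that sentence sits under the primary heading and assigns its own 0.025, so it contradicts the other sections.

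The defence is also right that the numerical effect is limited. At 21 + 20 = 41 the error is 0.02496, just inside 0.025. The peak needs N = 52, hence at least 32 primary subjects, and a true ORR of 0.11 in experienced subjects. Sizes 22 to 25 all stay below 0.025. If the combined test were run despite a failed Stage 1, the error could reach 0.038, but that would depart from the plan and deserves no weight.

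Much of the disagreement in Step 6 is dilution by a population with a lower assumed response rate. That would be unremarkable if only one test were decisive, which is why the status of the combined test has to be stated.

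On pembrolizumab, Section 3.1.2 enrols until 21 evaluable subjects are treated, so the mismatch would bite only if at least two extra subjects entered the population.

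**Conclusion.** The concern holds. Section 9.2 as written conflicts with Sections 4, 8 and 8.8, and following it does not guarantee the 0.025 stated for the ipilimumab arm. With the Stage 1 stop binding and ORR 0.11 throughout, the arm's error can rise from 0.0206 to as much as 0.0313, depending on a combined size the SAP does not fix. The excess is gone if experienced subjects respond at 0.05. Overall error control at 0.05 is not lost when the stop is binding. The fault is therefore the per-arm claim, the undefined status of the combined test, and a 0.11 null with no stated basis in ipilimumab-experienced subjects. It should be fixed before analysis, and the design itself needs no change.

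**What to change.** In Section 9.2, with Sections 8, 8.8 and 12 aligned:

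- Name the first-21 PIIEE test and the pembrolizumab test as the only primary tests.
- Either report the combined PIIEE and SIIIE ORR with an exact confidence interval and no test, or test it at 0.025 only if the first-21 test has rejected (fixed sequence). Under either option a false rejection in the arm requires the first-21 test to reject, so the error returns to 0.0206 and power stays at 77%.
- If the combined test is kept, state the basis for 0.11 in ipilimumab-experienced subjects.
- Minor: say that the pembrolizumab test uses the first 21 evaluable subjects, matching the 4-of-21 rule, with all evaluable subjects as supportive.

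The cost is SAP wording only; sample size and data collection are untouched. The price is that the combined result no longer carries a stand-alone confirmatory p-value.
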